4.1. Study Design

4.1.a. Detailed Description

Thirty opioid dependent and 30 healthy control participants will be recruited for the purposes of this study. Participants in each group will be randomized into either TMS or sham conditions (15 participants per group). Standard practice in electrophysiological studies commonly use a minimum of 15 participants per experimental group. All participants will complete consent protocols, and questionnaires regarding demographic and drug use history, and will be fitted with an EEG cap for ERP recording while they engage in a virtual T-maze choice task. A neuronavigation robot will position the TMS coil over a predetermined area of the brain, and TMS pulses will be delivered at 110% of the participants resting motor threshold at 10 Hz continuously over the predefined DLFPC target immediately before each of the 20 blocks of 10 trials, for a total of 1000 pulses and 200 trials (fixed at 100 reward and 100 no-reward). Identical parameters will be applied to the SHAM group with the exception that the TMS coil will be flipped 180° to mimic auditory stimulation.

4.1.b. Primary Purpose

Basic Science

4.1.c. Interventions

Type	Name	Description
Device (including sham)	TMS	Participants will be randomized into either the TMS (active) or SHAM group (coil flipped 180° to mimic auditory stimulation) during task performance. The TMS stimulator device used on our laboratory is a MagPro X100 with the Cool-B70 figure-of-eight coil (MagVenture, Falun, Denmark). The selection of stimulation intensity will be based on Resting Motor Threshold (rMT). In keeping within the safety guidelines, stimulation intensity will be set as 110% of rMT for the repetitive TMS. 50 rTMS pulses will be delivered at 110% of participants' resting motor threshold at 10 Hz continuously over the predefined DLFPC target immediately before each of the 20 blocks of 10 trials, for a total of 1000 pulses and 200 trials (fixed at 100 reward and 100 no-reward). Identical parameters will be applied to the SHAM group with the exception that the TMS coil will be flipped 180° to mimic auditory stimulation.

4.1.d. Study Phase

Early Phase 1 (or Phase 0)

Is this an NIH-defined Phase III Clinical Trial? Yes No

4.1.e. Intervention Model

Parallel

4.1.f. Masking

Yes No

Participant Care Provider Investigator Outcomes Assessor

4.1.g. Allocation

Randomized

4.2. Outcome Measures

Type	Name	Time Frame	Brief Description
------	------	------------	-------------------

Primary	Reward positivity amplitude	During intervention	Our project will utilize a highly sensitive biomarker of anterior cingulate cortex (ACC) control and reward function –the reward positivity– to image ACC function and monitor ACC modulation following TMS. Reward positivity amplitude will be determined by identifying the maximum absolute amplitude of the difference wave within a 200- to 400-ms window following feedback onset. The difference wave method, which was recommended in a recent metaanalysis of reward positivity studies [49], isolates the reward positivity from other ERP components. The reward positivity will be evaluated along front-central electrodes (Fz, FCz, Cz).
---------	-----------------------------	---------------------	---

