Title: Using Combined EEG and Non-invasive Brain Stimulation to Examine and Improve Reward Functioning in Opioid Use Disorder

NCT number: NCT04432493

Date: 12/04/2018

Statistical analysis. First, we predict that people with OUD will exhibit a truncated reward positivity elicited by monetary rewards, compared to healthy controls. This finding would indicate that OUD individuals are impaired at using normal rewards to develop internal representations of action value, and thus are impaired at using these action values for cognitive control. Second, we predict that repetitive TMS will lead to increases in dopamine release and neuronal activity in the ACC, thereby leading to a positive shift in the ACC valuation of monetary rewards in OUD as revealed by an increase in reward positivity amplitude in the active TMS group relative to the sham group. To test these predictions, we will conduct a 2×2 repeated measures analysis of variance with TMS (active vs sham) and Group (OUD vs. controls) as factors.

We anticipate the following results:

- *Aim 1:* A Group (OUD, control) by TMS (active, sham) interaction, where OUD participants in the sham condition will demonstrate an attenuated reward positivity signal relative to the control participants in the sham condition.
- *Aim 2:* A within-group main effect of TMS (active, sham) where participants receiving active TMS will demonstrate a larger reward positivity compared to participants in the sham condition. We also anticipate a 2-way TMS (active, sham) by Group (OUD, control) interaction, where control participants receiving the active TMS will demonstrate a larger reward positivity signal relative to the SHAM control group. We also anticipate OUD participants receiving active TMS will demonstrate a larger reward positivity relative to OUD SHAM.

Linear regression models will be used to compare groups while adjusting for potential confounds within each age group and for the whole sample while controlling for age and education. Post hoc analysis (e.g., Tukey HSD) will be performed when linear regression shows any significant main effects or interactions. In all comparisons, sex will be considered as a biological variable to assess trends to be explored further in the R01 longitudinal study.

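### Read literally, the primary score (maximum absolute amplitude) drops the sign of the reward positivity, although every SAP prediction is directional; the plan should state one signed score

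*Protocol*

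**What the plan says.** Protocol section 4.2 (Outcome Measures) names one primary outcome, reward positivity amplitude. It is obtained by "identifying the maximum absolute amplitude of the difference wave within a 200- to 400-ms window" after feedback, and "The reward positivity will be evaluated along front-central electrodes (Fz, FCz, Cz"). The section supports its approach by citation: "The difference wave method, which was recommended in a recent metaanalysis of reward positivity studies [49"]. It states no subtraction order and no sign convention.

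The SAP does not redefine the score. It enters it in a "repeated measures analysis of variance with TMS (active vs sham) and Group (OUD vs. controls) as factors". Its predictions all have a direction:

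- TMS is to produce a "positive shift in the ACC valuation of monetary rewards in OUD as revealed by an increase in reward positivity amplitude".
- Aim 1: "OUD participants in the sham condition will demonstrate an attenuated reward positivity signal relative to the control participants in the sham condition".
- Aim 2: "We also anticipate OUD participants receiving active TMS will demonstrate a larger reward positivity relative to OUD SHAM", with the same direction predicted for controls.

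**The concern.** A maximum taken over absolute values cannot tell a strong reward response from a strong reversed one. The hypotheses are about more or less of a positive response, so the score and the hypotheses do not match.

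Folding negative values upward also raises the lowest-amplitude cell most. By the SAP's own prediction that cell is OUD sham, which enters both the Aim 1 contrast and the OUD part of Aim 2. Raising it shrinks the OUD deficit and the apparent TMS gain in OUD. Because controls are folded less, it can also create a Group by TMS interaction on the score when the true TMS effect is the same in both groups.

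**Working it through.** **Plan's own figures.** The Protocol quotes 85% power for 60 participants (Statistical design and power) and .82 for a sample of 15 (Recruitment and Retention Plan). Neither comes with an amplitude, an SD or a numerical effect size, so there is no figure for this score to reproduce. The point does not rest on them.

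**Inputs from the documents.** The scoring rule and window (section 4.2); 15 participants per cell (section 4.1.a); 100 trials per feedback type (section 4.1.a: "for a total of 1000 pulses and 200 trials (fixed at 100 reward and 100 no-reward")).

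**Assumed inputs.** All amplitudes and SDs, and single-trial noise SD of 6, 8 or 12 µV. The noise SD of the difference wave is the single-trial SD × √(2/100), that is 0.85, 1.13 or 1.70 µV.

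**Step 1: the sign is lost by definition.** max|w| equals max|−w|. Noise-free waves peaking at +6, +3, −3 and −6 score 6, 3, 3 and 6. Keeping the sign of the extremum gives +6, +3, −3 and −6. The positive peak scores the two reversed waves close to zero.

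**Step 2: effect on a group gap, without noise.** For true amplitudes A with mean m and SD s:

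- share negative = Φ(−m/s)
- E|A| = s√(2/π)·exp(−m²/2s²) + m[1 − 2Φ(−m/s)]
- positive peak: E[max(A,0)] = (m + E|A|)/2

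With s = 3.8, s√(2/π) = 3.03.

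- m = 5: 3.03 × 0.421 + 5 × (1 − 2 × 0.094) = 1.28 + 4.06 ≈ 5.33
- m = 2: 3.03 × 0.871 + 2 × (1 − 2 × 0.299) = 2.64 + 0.80 = 3.44

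Folding adds 0.33 to the higher mean and 1.44 to the lower. The true gap of 3.0 reads 1.89. The positive peak gives (3.0 + 1.89)/2 = 2.45, so it recovers half of the lost gap.

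| Means, SD (µV) | Share negative | True gap | Absolute score |
|---|---|---|---|
| 5 v 2, 3.8 | 9%, 30% | 3.0 | 1.89 |
| 8 v 5, 3.8 | 2%, 9% | 3.0 | 2.71 |
| 10 v 7, 3.8 | 0.4%, 3% | 3.0 | 2.91 |
| 5 v 3.4, 2 | 0.6%, 4% | 1.6 | 1.53 |

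The standardised effect is the same throughout (3.0/3.8 = 0.79; 1.6/2 = 0.80). Only the distance from zero changes.

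**Step 3: spurious interaction.** Let TMS add 3 µV in both groups (controls 5 to 8, OUD 2 to 5, SD 3.8). The absolute score reads the OUD gain as 1.89 and the control gain as 2.71. The interaction is 1.89 − 2.71 = −0.82, where the truth is 0. For the positive peak it is half of that, −0.41.

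**Step 4: power, by simulation.** A Gaussian component at 290 ms (SD 40 ms) was sampled at 500 Hz with flat or 1/f noise up to 20 Hz, equal noise in all cells, and two-sided tests at 0.05.

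| Contrast | Absolute | Signed positive peak |
|---|---|---|
| Control sham v OUD sham, 5 v 2, 15 v 15 | 33–36% | 47–50% |
| OUD active v OUD sham, 5 v 2, 15 v 15 | 31–37% | 44–50% |
| Group main effect in the 2×2 of step 3 | 69–75% | 78–82% |
| False interaction rejected (nominal 5%) | 8–9% | about 6% |
| 5 v 3.4, SD 2, 30 v 30 | 57–80% | 60–81% |

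At 10 v 7 the difference is 0–1 point. With the sign kept at the extremum, the interaction is rejected 4.7–5.5% of the time.

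**Step 5: different assumptions.** With between-participant SD 2.2, smooth noise SD 1.0 and 30 v 30, power for the absolute v sign-kept score is 0.87 v 0.87 at 6 v 4, 0.81 v 0.85 at 4 v 2, 0.66 v 0.84 at 3 v 1, and 0.29 v 0.82 at 2 v 0. For true means of −2 v 0, the absolute score gives group means of 3.12 v 2.60, so the reversed group looks larger.

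**The case against.** The strongest reply is that this turns on one word. The component is called a positivity and the SAP predicts an increase, so the intended polarity is plain. 'Absolute' may only tell the analyst how to find the extremum, or may mean measured from baseline. Either reading keeps the sign and removes most of the problem. That stands as a limit on the point, but neither reading is written down, and the citation is offered for the difference-wave method, not for an unsigned peak.

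A second reply is that the SAP predicts attenuated responses, not reversed ones, and nothing in the documents suggests that 30% of OUD amplitudes are negative. This also stands. That share follows from the assumed 5 v 2 with SD 3.8. At the same standardised effect with 5 v 3.4 and SD 2, the power loss is 1–3 points.

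Third, the missing subtraction order does no extra harm under the literal reading, because max|w| does not depend on it. Correct: it matters only once the sign is kept, so it belongs in the fix and is not a second defect.

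Two larger claims are tempting, and the documents support neither:

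- *A 30 v 30 comparison loses roughly 14 to 19 points of power.* That range comes from simulating 5 v 2 at 30 per side (from .817 − .674 = .143 to .761 − .568 = .193). In the matching 2×2, 5 and 2 are the two sham cells, with 15 participants each. The 30 v 30 margin pools 5 and 8 against 2 and 5, and loses about 7–9 points.
- *The score inflates type I error.* Any peak score rises with residual noise, so unequal usable-trial counts could bias a contrast. The documents give no sign that data quality will differ by group or arm, so this is not a ground for the point.

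**Conclusion.** The point holds as a mismatch between the stated scoring rule and the directional hypotheses. It is more than missing detail: the rule as written gives a worse answer wherever responses are small or reversed.

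Its size cannot be fixed from the documents. With many negative amplitudes (5 v 2, SD 3.8), the gap shrinks from 3.0 to about 1.9 µV. The sham contrast loses about 14 points of power and the Group main effect about 7–9. A spurious interaction of about 0.8 µV is rejected 8–9% of the time. The sham contrast is at about 50% or less under either score, so the sign is not its only limit. When responses lie well above zero, the loss is 0–3 points.

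A reader might infer that the recordings have been or will be scored unsigned. The documents do not show that; they show only that the written rule would do so. The change should be made, with medium confidence in its practical importance.

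**What to change.** In Protocol section 4.2, and in identical words in the SAP:

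1. Delete 'absolute' and define the difference wave as reward minus no-reward.
2. Score one signed value per participant, choosing one of two rules: the extremum in 200–400 ms with its sign kept, or the signed positive peak in that window.
3. Say how Fz, FCz and Cz yield that single value. This is a clarification only.
4. Adopt the definition before any group or arm comparison is run, and apply it to all participants, including those already recorded.
5. Add, as a sensitivity analysis, signed mean amplitude in a window fixed before any such comparison.

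The two rules differ. The sign-kept extremum scores a reversed response as negative, but in a noisy record the largest deflection may be noise of the wrong sign. The positive peak floors reversed responses near zero, so it recovers only half of the lost gap and keeps about half of the spurious interaction. In the settings simulated, the positive peak was never more than 1 point of power below the absolute score.

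The cost is the re-scoring of recorded EEG (the cumulative table in Protocol section 2.9 lists 23 enrolled) and slightly less comparability with any earlier results scored by the absolute rule. Because the primary score is being changed with recruitment under way, the date of the change, and the fact that no comparison had yet been run, should be recorded.

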4.3. Statistical Design and Power

[Statistical_design_and_power_R21_opioid.pdf](#)

4.4. Subject Participation Duration

Subjects will participate in one session lasting up to 2 hours.

4.5. Will the study use an FDA-regulated intervention?

Yes No

4.5.a. If yes, describe the availability of Investigational Product (IP) and Investigational New Drug (IND)/ Investigational Device Exemption (IDE) status

4.6. Is this an applicable clinical trial under FDAAA? (SEE SECTION 6.6)

4.7. Dissemination Plan

[Dissemination_R21_opioid.pdf](#)

Statistical design and power

This study will adopt a randomized sham-controlled design. Participants will be randomized into either the TMS (active) or SHAM group (coil flipped 180° to mimic auditory stimulation) during task performance. Thirty dependent opioid users (OUD group) and 30 controls with no history of alcohol or drug dependence will be recruited for this study (15 participants per TMS/sham group). Standard practice in electrophysiological studies commonly use a minimum of 15 participants per experimental group. Further, based on previous work [27-29] an estimated 60 subjects in total will be required to identify a moderate to large main effect on the reward positivity, critical $F(4, 55) = 4.01, p = 0.05, 85\%$ power.

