Inclusion of Children: Previously, NIH considered individuals under 21 years of age to be children, but this has now changed (children are now defined as under 18; see NIH NOT-OD-16-010). We will be including 18- 55 year olds in our study. Thus, we will not be including children in this project. Note that the investigators have had ample previous experience working with participants in this age range (e.g., those 18-20 years old), and all study procedures are appropriate for this age range. Children below age 18 will not be studied in this project because a separate age-specific project is warranted, and even preferred, given that normal developmental changes in cognitive control processes during childhood are prominent, but not yet well understood.

Recruitment and Retention Plan

In total, we plan to collect 60 participants (30 opioid users, 30 controls) over 2 years for the proposed study. Participants will be randomized into TMS or sham groups (15 participants per group). Standard practice in electrophysiological studies commonly use a minimum of 15 participants per experimental group. Further, basing the analyses on our previous results, a priori power analysis indicated that a sample size of 15 would be sufficient to detect a significant effect with a power of .82 and an alpha of .05. Potential OUD participants will be recruited through the community using an 'expression of interest' flyer. The flyer will be distributed throughout pharmacies, clinics, universities, community recreation venues, via email, social networking websites and possibly through media outlets such as through newspapers and radio. Control participants will be recruited using personal networks, advertisements on volunteer job sites and by placing flyers in local community settings.

TIMELINE

Months 1–18. Aim 1 and Aim 2 (initiation) Recruiting and testing control and OUD subjects with our virtual T-maze task with Ri-TMS capabilities, which is already developed.

Months 18–24. Completion of Aim 1 and Aim 2. Analyse data from Months 1–18 for publication. Prepare and submit manuscript for publication.

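### The power statement in Protocol 4.3 pairs F(4, 55) with a critical value for 1 numerator df, and its 85% is for a main effect, not for the interaction or 15 v 15 contrasts in the SAP aims

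*Protocol*

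**What the plan says.** Two power statements stand behind N = 60.

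- Protocol 4.3, Statistical design and power (the attached text is printed after the 4.7 heading): "an estimated 60 subjects in total will be required to identify a moderate to large main effect on the reward positivity", followed by "critical $F(4, 55) = 4.01, p = 0.05" and 85% power. No f, d, mean difference or SD is given.
- Protocol, Recruitment and Retention Plan (2.5): "a priori power analysis indicated that a sample size of 15 would be sufficient to detect a significant effect with a power of .82", at alpha .05. No test, comparison or effect size is given.

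The design is in Protocol 4.1.a: "Participants in each group will be randomized into either TMS or sham conditions (15 participants per group". That makes four between-person cells of 15, or 30 v 30 on each margin.

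The analysis is in the SAP: "we will conduct a 2×2 repeated measures analysis of variance with TMS (active vs sham) and Group (OUD vs. controls) as factors". Aim 1 is written as "A Group (OUD, control) by TMS (active, sham) interaction", and is explained by the prediction that "OUD participants in the sham condition will demonstrate an attenuated reward positivity signal relative to the control participants in the sham condition". Aim 2 names a TMS main effect, a second TMS by Group interaction, and active v sham comparisons within each group, for example "control participants receiving the active TMS will demonstrate a larger reward positivity signal relative to the SHAM control group". The SAP states no power for any of these.

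**The concern.** A critical value follows from alpha and the two degrees of freedom, so the printed pair can be checked without knowing the effect size. It fails that check. As no effect size is stated, a reader cannot tell from 4.3 which test was powered or for what effect.

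The second issue is scope. Protocol 4.3 speaks of a main effect, but Aim 1 and part of Aim 2 rest on an interaction and on comparisons of 15 with 15. If .82 to .85 is taken as the power of those tests, a non-significant interaction or cell contrast could be reported as evidence of no effect when the study had limited ability to detect one.

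**Working it through.** **Inputs.** From the documents: N = 60, four cells of 15, alpha 0.05, power 85%, printed F(4, 55) = 4.01, and a main effect described only as moderate to large. Assumed: two-sided tests, equal cells, common SD, one reward positivity value per person, no covariates.

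**1. The printed critical value.** The 5% upper points of the central F distribution are:

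| df | 5% critical F |
|---|---|
| (4, 55) | 2.540 |
| (1, 55) | 4.016 |
| (1, 56) | 4.013 |
| (1, 57) | 4.010 |
| (1, 58) | 4.007 |

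On (4, 55), 4.01 has p = 0.006. Other common alphas do not give it either: 3.03 at 0.025, 3.68 at 0.01, 4.18 at 0.005. In a 2×2 with four between-person cells and N = 60, each effect has df (1, 60 − 4) = (1, 56), and the critical value 4.013 rounds to 4.01.

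**2. The 85%.** Noncentral F with λ = N·f², and d = 2f for two equal halves.

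- df (1, 56), f = 0.40: λ = 60 × 0.16 = 9.6, power 86.1%.
- df (1, 56), f = 0.394 (d = 0.79): λ = 9.3, power 85.0%.
- df (1, 56), f = 0.25: λ = 3.75, power 48%.
- df (4, 55), f = 0.40, using its correct critical value of 2.54: power 65%. This test needs f = 0.494 for 85%.

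The stated N and power therefore reproduce for a 1-df main effect at the large end of the stated description. A 4-df test at f = 0.40 does not reproduce them.

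**3. A 15 v 15 contrast.** Noncentrality = d·√(15/2). At d = 0.787 this is 0.787 × 2.739 = 2.16. Unadjusted power is 55% on 28 df, or 56% with the pooled 56 df. For 85%, d must be 1.13 (28 df) or 1.11 (56 df).

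**4. The Group×TMS interaction.** The standard error of a difference of differences is √(4/15) = 0.516 SD. At 0.787 SD the noncentrality is 0.787/0.516 = 1.52, and power is 32%. At 1.57 SD it is 3.05, and power is 85%.

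**5. Sensitivity to the unstated effect size.**

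| d | 30 v 30 main effect | 15 v 15, unadjusted | Interaction of the same SD size |
|---|---|---|---|
| 0.50 | 48% | 26-27% | 16% |
| 0.79 | 85% | 55-56% | 32% |
| 0.80 | 86% | 56-58% | 33% |

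**6. Sensitivity to the cell means.** Hold the average TMS effect at 0.79, so that the TMS main effect keeps 85%. Contrasts are unadjusted on 56 df.

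| TMS effect, one group / other group | Active v sham within each | Interaction |
|---|---|---|
| 0.79 / 0.79 | 56% / 56% | none present |
| 1.18 / 0.39 | 89% / 19% | 32% |
| 1.57 / 0 | 99% / no effect | 85% |

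The smaller of the two effects cannot exceed their average. So if the average is 0.79, at least one of the two active v sham contrasts has power of at most about 56%.

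**7. The .82 with 15.** Read as 15 v 15 (28 df), .82 requires d = 1.09. Read as a one-sample or paired test with n = 15, it requires a standardised effect of 0.80.

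**The case against.** The strongest reply is that this is a misprint with no effect on the design. A sample-size search for a 1-df effect in four cells at f = 0.40 and 85% power gives N = 59, error df 59 − 4 = 55 and critical F 4.016. That value truncates to 4.01, and 59 rounds up to 60 for equal cells. On that account the 55 is right and only the 4 is a slip. This is an inference, but it fits the printed figures well. A reader might instead infer that (4, 55) must come from a four-term regression, since 60 − 4 − 1 = 55. The documents do not establish that either. Both accounts leave the printed pair wrong.

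It is also fair to say that 4.3 claims power only for a main effect, that the SAP does predict main effects, and that powering on one is a legitimate choice in a small basic-science study. This stands, and it is why the point concerns scope rather than N. A reader might go further and infer that the interaction and cell contrasts are underpowered whatever the truth. The documents do not support that. They state no cell means, and under the 1.57 / 0 pattern the interaction has 85% and one contrast 99%. Giving the interaction the same Cohen's f as the main effect also yields 85%, but that amounts to the same 1.57 SD difference of differences.

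A reader might infer that .82 contradicts 85%, because 15 v 15 implies d of 1.09 rather than 0.79. The one-sample or paired reading gives 0.80, and the reward positivity is itself a within-person difference wave, so a conflict is not shown. The scales differ and the trial is parallel-group, so agreement is not shown either.

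Finally, Tukey adjustment over all pairs of four cells would lower the 15 v 15 figure at d = 0.79 to about 32%. The SAP names Tukey HSD only as an example, to follow a significant regression result, so that figure is conditional and is not relied on here.

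**Conclusion.** The concern holds in two limited respects. First, the df and critical value in 4.3 cannot belong to the same 5% test: 2.54 is correct for (4, 55), and 4.01 needs 1 numerator df. The numerator df is the likely error. Second, the 85% applies to a 30 v 30 main effect of about f = 0.39 to 0.40 and gives no assurance for the interaction or the 15 v 15 contrasts. At the implied d of 0.79 those have about 32% (difference of differences of the same SD size) and 55-56% (unadjusted). The interaction reaches 85% only if the TMS effects in the two groups differ by about 1.57 SD.

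These power figures rest on a back-solved effect size and on the assumptions listed with the inputs. The critical-value finding rests on neither. Nothing here shows that N = 60 is wrong for the main effect. The .82 cannot be checked as written. The correction should be made because it changes how a null result on the interaction or a cell contrast may be read.

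**What to change.** In Protocol 4.3:

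- Replace the printed pair with the df and critical value of the test actually used, and state its effect size and source. If the test is a 2×2 main effect with N = 60, the pair is df (1, 56) and critical F 4.01. The effect size should be the sponsor's own, not the value back-solved here.
- Limit the claim, for example: the 85% applies to a 30 v 30 main effect (TMS or Group) and does not cover the Group×TMS interaction or the 15 v 15 contrasts.
- Give the power of the interaction and the 15 v 15 contrasts under stated cell means and the chosen multiplicity method. If no single pattern can be defended, show a range.

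In the Recruitment and Retention Plan, give the test and effect size behind .82, or delete the sentence.

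The cost is rewording two paragraphs and retrieving the original calculation. N, conduct and analysis do not change. The downside is that the stated power for the interaction and cell contrasts may look less favourable than .82 to .85.
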